## **2.8 PROHIBITED AND RESTRICTED THERAPIES**

Treatment with certain restricted concomitant medications is allowed once during study to treat acute HS exacerbation, including:

- Systemic therapies with known effectiveness in HS, including corticosteroids, retinoids, or anti-androgen (hormonal) therapies.
- Intralesional/topical steroids
- Laser/light therapies

The use of rescue medications for worsening HS is to be reported in the electronic data capture system. A second flare up of disease and subsequent use of a second rescue therapy for any patient will result in the patient being treated as a non-responder for the purposes of data analysis.

The following concomitant therapies are *prohibited* for the entire duration of the trial:

- Biologics that target IL-1 or TNF-alpha
- Live virus vaccines
- Investigational agents other than bermekimab

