## 8.2 Study Endpoints

The primary endpoint of this study is the safety and tolerability of bermekimab at 400 mg weekly subcutaneous dose.

The secondary endpoints include:

- Hidradenitis Suppurativa Clinical Response (HiSCR) score (baseline to visit 13). For this score patients are defined as achievers or non-achievers. The positive HiSCR score is defined as a  $\geq 50\%$  reduction in inflammatory lesion AN count (sum of abscesses and inflammatory nodules), and no increase in abscesses or draining fistulas in HS compared with the lesions counted on visit 1. The HiSCR score, including inflammatory lesion count, will be measured on visits 1, 3, 5, 7, 9, 11, 13 and 14.
- Pharmacokinetics (PK) (baseline to visit 13). An enzyme-linked immunosorbent assay (ELISA) has been developed to specifically measure bermekimab levels in human plasma. Blood will be drawn into a single 6 ml collection tube at each PK collection time point (sample collection is pre-dose at visit 1, visit 3, visit 5, visit 9 and visit 13). These samples will be collected per the study lab manual and immediately shipped to the Sponsor for PK analysis. The PK samples will also be used to test for the presence of antibodies against bermekimab.
- Physician's Global Assessment (PGA) (baseline to visit 13). This is defined as: a) clear when the total number of abscesses is 0, the total number of draining fistulas is 0, the total number of inflammatory nodules is 0 and the total number of non-inflammatory nodules is 0; b) minimal when the total number of abscesses is 0, the total number of draining fistulas is 0, the total number of inflammatory nodules is 0 and there is presence of non-inflammatory nodules; c) mild when the total number of abscesses is 0, the total number of draining fistulas is 0, and the total number of inflammatory nodules is 1-4, or when there is presence of one abscess or draining fistula and absence of any inflammatory nodules; d) moderate when the total number of abscesses is 0, the total number of draining fistulas is 0 and the total number of inflammatory nodules is at least 5; or when there is presence of one abscess or draining fistula and at least one inflammatory nodule; or when there are 2-5 abscesses or draining fistulas and fewer than 10 inflammatory nodules; e) severe when the total number of abscesses or draining fistulas is 2-5 and the total number of inflammatory nodules is at least 10; and f) very severe when there

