#### **10.5.3 Analysis of Secondary Endpoints:**

Proportion of patients achieving a positive Hidradenitis Suppurativa Clinical Response (HiSCR) score after 13 weeks will be summarized by treatment group (and pooled overall population). The corresponding 95% confidence interval (CI) for the point estimate will be provided. Subjects previously enrolled in the 200mg/weekly dosing cohort who have received *two or fewer* bermekimab injections (2 x 200mg doses) before beginning the 400mg weekly doses will be included for data analysis together with those receiving all doses at 400mg/weekly. Patients who have received more than 2 bermekimab injections of 200mg may enter the 400mg/week arm; however, only patients who have received *two or fewer* bermekimab injections will be included in the data analysis.

Change in outcomes from baseline to week 13 (VAS for disease, VAS for pain, DLQI, inflammatory lesion count, PGA, Disease Activity Score, and modified Sartorius score) will be summarized using descriptive statistics (n, mean, standard deviation, median, minimum and maximum value). The 95% CI of the mean change from baseline will be provided.

A rank-ordered analysis will be performed for the total abscess and inflammatory nodule count (ranked at 0, 1 or 2) and reduction in pain score (categorized as  $\geq 30\%$  reduction on pain score among patients with baseline score of  $\geq 3$ ). The change in modified Sartorius score will be dichotomized at 4 ( $\leq 4$  least severe disease, higher indicates severe disease). Number and percent under each treatment group (and pooled overall) will be summarized.

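### The rescue rule cannot be applied to the seven mean-change outcomes, so visit 13 values measured after effective HS rescue can be read as change on bermekimab

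*Combined protocol and SAP*

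**What the plan says.** On rescue, section 2.8 states: "Treatment with certain restricted concomitant medications is allowed once during study to treat acute HS exacerbation". The permitted treatments include "Systemic therapies with known effectiveness in HS, including corticosteroids, retinoids, or anti-androgen (hormonal) therapies", as well as intralesional or topical steroids and laser or light therapy. Rescue use is entered in the electronic data capture system. The only analysis consequence follows a second flare with a second rescue, when the patient is "treated as a non-responder for the purposes of data analysis". No consequence is given for a first rescue.

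On outcomes, section 8.2 defines HiSCR as binary: "For this score patients are defined as achievers or non-achievers". Section 10.5.3 then takes seven further outcomes ("VAS for disease, VAS for pain, DLQI, inflammatory lesion count, PGA, Disease Activity Score, and modified Sartorius score) will be summarized using descriptive statistics") and adds: "The 95% CI of the mean change from baseline will be provided". Rescue is not mentioned there.

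On who and what is counted, section 10.3.1 analyses the secondary endpoints in the safety set (everyone dosed) and in the per protocol set (everyone with the visit 1 and visit 13 disease assessments). Section 10.5 summarises the observations available.

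**The concern.** Non-responder is a category. It settles the HiSCR table but supplies no value for a mean change in lesion count, pain or DLQI. Unless another rule intervenes, whatever is recorded at visit 13 goes into the mean, including scores taken after a corticosteroid course or other therapy that the protocol itself regards as effective in HS.

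The study has no control arm in which a similar rescue effect would show up. The patients concerned have flared on study drug, so any help they had from rescue would be credited to bermekimab. The tables could also pull apart: a twice-rescued patient is a HiSCR failure by rule, while the same patient's lesion count, on which HiSCR is built, enters the mean as observed. Section 1.2 says the study is meant to prepare for randomised studies of subcutaneous dosing, so an inflated mean change could carry into their planning.

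**Working it through.** The plan states no figure on this point, so there is none to reproduce. The check has two parts.

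**1. Does any section supply a rule for post-rescue values in the change outcomes?**

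- Section 2.8: responder status only, and only after a second rescue.
- Section 5.3: a second rescue is not itself a listed reason to stop therapy (the investigator may stop for clinical progression), so visit 13 can follow it.
- Section 10.3.1: neither set excludes rescued patients. The per protocol set selects on completed assessments, so it is not a rescue sensitivity analysis.
- Section 10.5: available observations are used; no replacement or censoring is described.
- Section 10.5.3: seven mean-change outcomes (VAS disease, VAS pain, DLQI, inflammatory lesion count, PGA, Disease Activity Score, modified Sartorius), with no mention of rescue. HADS is an eighth change endpoint in sections 3.1 and 8.2 but is absent from this list.

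No section closes the gap.

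**2. How much could it matter?**

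Inputs from the synopsis: n = 10 per group, 20 in total. One patient's weight in a mean is 1/n: 1/10 = 10% per group, 1/20 = 5% pooled.

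Let k be the number of rescued patients in the mean and f the share of each such patient's change that is due to rescue. The shift in the mean, in units of one rescued patient's whole change, is (k/n) × f. Both k and f are assumptions, since the documents give neither; the range k = 1 to 3 and f = 0.25 to 1.0 gives:

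| k | n=10, f=0.25 | n=10, f=1.0 | n=20, f=0.25 | n=20, f=1.0 |
|---|---|---|---|---|
| 1 | 0.025 | 0.10 | 0.0125 | 0.05 |
| 2 | 0.05 | 0.20 | 0.025 | 0.10 |
| 3 | 0.075 | 0.30 | 0.0375 | 0.15 |

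Illustration in lesions (all values assumed): abscess and nodule count 12 at visit 1, still 12 before rescue, 2 at visit 13, with the whole fall of 10 due to rescue.

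- One patient: −10/10 = −1.0 in the group mean; −10/20 = −0.5 in the pooled mean.
- Two in one group: −20/10 = −2.0.
- With an assumed SD of change of 5, the group SE is 5/√10 = 1.58, so one such patient moves the mean by 1.0/1.58 = 0.63 SE. If only a quarter of the fall is due to rescue, the shift is 0.25/1.58 = 0.16 SE.

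The illustration with f = 1 is deliberately extreme: it assumes no drug effect and no spontaneous resolution.

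**The case against.** The strongest reply is that silence is not an instruction. The non-responder wording is not confined to HiSCR, section 10 calls itself the basis for a SAP, and section 10.5.5 defers details to that SAP. This stands to the extent that the plan nowhere states that post-rescue values are used. But a broad phrase still gives no number for a mean, and the text available contains nothing that removes or replaces those values.

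A reader might go further and infer that a twice-rescued patient is a failure in one table and a success in seven others, with full improvement credited to the drug. The documents do not support that. The mean-change tables classify nobody as a success. A patient who has flared twice may be at or above baseline at visit 13, and section 1.2 says flares typically last 3–5 days, so improvement after rescue may be natural resolution.

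Three more points stand in part:

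- Summarising observed values regardless of rescue is a legitimate choice if labelled. That is a reason to keep it, not to leave it unlabelled.
- Section 10.5.3 also plans categorical summaries of lesion count, pain reduction and Sartorius score. A non-responder rule could work for the pain response, but the plan does not say so, and it would not touch the means.
- These are descriptive secondary outcomes in an open-label convenience sample with a safety primary endpoint, and no rescue rule would make a single-arm change isolate the drug effect. That limits the weight of the point. Rescue differs from the other sources of change, though, in being recorded and separable.

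**Conclusion.** The gap is real and should be closed, but it is moderate. The rescue rule has no meaning for the seven mean-change outcomes, and neither analysis set removes post-rescue values, so such values can enter the means and their intervals and be read as change on bermekimab. A permitted first rescue raises the same issue as a second.

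The likely direction is towards apparent benefit, because the rescue therapies are described as effective in HS; the documents do not demonstrate it. The size is unknown: rescue rate, SD and rescue benefit are all missing. What is firm is the weight of one patient, 10% of a group mean and 5% of the pooled mean at the planned sizes. Under the assumed ranges above, the shift is 0.025 to 0.30 of one rescued patient's change per group and 0.0125 to 0.15 pooled. The primary safety endpoint is unaffected.

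A reader might also conclude that change after a second rescue must be set to zero. The documents do not require that; it is one debatable single imputation, too favourable for a patient who would have been worse than baseline.

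**What to change.** In section 10.5.3:

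1. Keep the all-observed summary and label it as including values measured after rescue.
2. Prespecify a companion table for each change outcome, HADS included, in which values after any rescue, first or second, are replaced by the last scheduled assessment before that patient's first rescue (visits 1, 3, 5, 7, 9, 11 or 13). Use the same patients as the observed table, so that the two differ only in the handling of rescue.
3. List rescued patients with rescue dates from the data capture system.
4. State whether the non-responder rule applies to the categorical summaries.

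Zero change after a second rescue may be shown as a further sensitivity analysis but should not be mandated. The synopsis and section 2.8 allow restricted medication once, while section 2.8 also provides for a second rescue; these statements should be reconciled, and the analysis rule should work either way.

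The cost is one extra table and a listing from data already collected, and possibly less favourable means. The companion table has the usual limits of single imputation. Assessments are 14 days apart, so the pre-rescue value may be about two weeks old when rescue starts, and older still relative to visit 13. It may catch a flare at its peak, and the CI treats it as observed. A rescue before visit 3 returns the baseline value, that is, zero change. For these reasons it should accompany the observed summary and not replace it. The rule should be fixed before results are reviewed, since the study is open label. Patient care is unchanged.

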## **3. STUDY DESIGN AND OBJECTIVES**

Phase 2, Open label, multicenter study of two dose cohorts of bermekimab in patients naïve to or having failed prior anti-TNF therapy with moderate to severe Hidradenitis Suppurativa. Bermekimab administered subcutaneously at a dose of 400 mg weekly (13 doses). Patients will be followed for 13 weeks to allow for assessment of safety and preliminary efficacy.

The study protocol will be approved by the Institutional Review Board (IRB) or the Ethics Committee (EC) of the participating study sites. Depending on the participating countries both local and central IRB/EC approvals will be granted. The study will be registered at [www.clinicaltrials.gov](http://www.clinicaltrials.gov) before the enrollment of the first patient. The trial will be conducted in compliance with the protocol, GCP, and all applicable regulatory requirements.

### **3.1 Study Endpoints**

#### ***Primary Endpoint:***

- Safety and Tolerability

#### ***Secondary Endpoints:***

- Hidradenitis Suppurativa Clinical Response (HiSCR) from baseline (visit 1) to visit 13.
- Assessment of Pharmacokinetics (PK)
- Change in patient reported outcomes from baseline (visit 1) to visit 13 (VAS for disease, VAS for pain, DLQI).
- Change in Physician's Global Assessment (PGA), Disease Activity Score, and modified Sartorius score from baseline (visit 1) to visit 13.
- Change in inflammatory lesion (abscesses and inflammatory nodules) count from baseline (visit 1) to visit 13.
- Change from baseline (visit 1) to visit 13 in Hospital Anxiety Depression Scale (HADS).

## 4. ELIGIBILITY CRITERIA

### 4.1 INCLUSION CRITERIA

**No waivers/exemptions will be granted for protocol inclusion/exclusion criteria.**

Subjects are included in the study if they meet all of the following criteria:

- Written informed consent provided by the patient.
- Male or female, age  $\geq 18$  years.
- For group A, patients must have received and failed anti-TNF therapy. For group B, subjects must not have received any prior treatment with any anti-TNF therapy.
- Patients who have received 200mg dose of bermekimab in this study are eligible to begin receiving 400mg dose starting with the patient's next scheduled visit for the remainder of his/her treatment plan.
- Diagnosis of HS for at least 1 year prior to screening.
- HS affecting at least two distinct anatomic areas, one of which is Hurley II or III stage.
- A total body count of abscesses and inflammatory nodules (AN) of at least 3
- Full understanding of the procedures of the study protocol and willingness to comply with them.
- In case of female patients of childbearing potential, willingness to use one method of contraception of high efficacy during the entire study period. This method can be hormonal contraceptives or one of the following: condoms, diaphragm, or an intrauterine device. Women of non-childbearing potential include those considered to have a medical history that indicates that pregnancy is not a reasonable risk, including post-menopausal women and those with a history of hysterectomy.

#### 4.2 EXCLUSION CRITERIA

Subjects will be excluded from the study if they meet any of the following criteria:

- Age below 18 years.
- Receipt of oral antibiotic treatment for HS within 28 days prior to screening.
- Receipt of prescription topical therapies for the treatment of HS within 14 days prior to screening, and systemic therapies for HS (immunosuppressants, corticosteroids, retinoids, or hormonal therapies) within 28 days prior to screening.
- History of treatment with bermekimab for any reason EXCEPT patients previously treated with 200mg bermekimab dose in the previous version(s) of this study.
- History of severe allergic or anaphylactic reactions to human, humanized, chimeric, or murine monoclonal antibodies.
- Administration of any live (attenuated) vaccine over the last 4 weeks.
- New intake of opioid analgesics starting within 14 days prior to screening.
- Major surgery (requiring general anesthesia or respiratory assistance) within 28 days prior to visit 1, Day 0 of start of study drug.
- Hepatic dysfunction defined as any value of transaminases, of  $\gamma$ -glutamyl transpeptidase ( $\gamma$ GT) or of total bilirubin  $> 3 \times$  upper normal limit
- Stage C Child-Pugh liver cirrhosis.
- Chronic infection by the human immunodeficiency virus (HIV), hepatitis B virus (HBV) and hepatitis C virus (HCV).
- Neutropenia defined as  $<1,000$  neutrophils/mm^3.
- Pregnancy or lactation.

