## 5. TREATMENT PLAN

### 5.1 STUDY PROCEDURES

**Screening (maximum 21 days):** The screening period begins once the informed consent is signed.

- Informed Consent
- Demographics
- Medical History
- Concomitant Medications
- Physical Exam
- Vital Signs (blood pressure, pulse, oxygen saturation, respiratory rate and body temperature)
- Height
- Weight
- Body Mass Index (BMI) [BMI= weight (kg)/height (m^2)]
- Blood Draw:
  - Chemistry panel: Albumin, Alkaline Phosphatase, ALT, AST, GGT, Bicarbonate (CO2), Calcium, Chloride, Creatinine, Glucose, Potassium, Sodium, Total Bilirubin, Total Protein, Urea Nitrogen
  - Hematology Panel: Complete Blood Count (CBC) with differential and platelets
  - Infectious disease screening: HIV antibody, Hepatitis C antibody, Hepatitis B panel (HBsAg, anti-HBc, anti-HBs), and interferon gamma release assay (IGRA)
  - Serum pregnancy test for WOCBP
  - Inflammation Markers: CRP (C-Reactive Protein), ESR (Erythrocyte Sedimentation Rate)

Visit 1 (day 0, must occur within 21 days of signing informed consent):

- ***At least 45 minutes before injection:*** Remove syringe from refrigeration and lay flat; allow to warm to room temperature. Do not heat
- Pre-injection
  - Physical Exam
  - DLQI

- Urine pregnancy
- HISCR
- PGA
- Disease Activity Score
- Modified Sartorius
- HADS
- VAS for disease
- VAS for pain
- Vital signs (blood pressure, pulse, oxygen saturation, respiratory rate and body temperature)
- Blood draw for PK and biomarker analysis
- Bermekimab subcutaneous injection, in accordance with injection site determined by BMI at Screening
- 1 hour monitoring for injection reaction
- Vital signs (blood pressure, pulse, oxygen saturation, respiratory rate and body temperature) one hour post injection (70 +/- 10 minutes)
- Adverse event monitoring
- Concomitant medications/treatments

Visit 2 (day 7 +/-2):

- ***At least 45 minutes before injection:*** Remove syringe from refrigeration and lay flat; allow to warm to room temperature. Do not heat
- Pre-injection
  - Urine pregnancy
  - Vital signs (blood pressure, pulse, oxygen saturation, respiratory rate and body temperature)
- Bermekimab subcutaneous injection, in accordance with injection site determined by BMI at Screening
- 1 hour monitoring for injection reaction
- Vital signs (blood pressure, pulse, oxygen saturation, respiratory rate and body temperature) one hour post injection (70 +/- 10 minutes)
- Adverse event monitoring

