## 8. STUDY VARIABLES

### 8.1 Demographic and Disease Characteristics

Demographic characteristics will include standard demography (age, sex, race, height, weight, and BMI) medical history, medication history, and prior biologic use for each patient. Characteristics of the patients with hidradenitis suppurativa, including duration of disease, baseline disease severity scores (HiSCR, modified Sartorius score, and physician's global assessment), baseline inflammatory lesion counts (abscesses and inflammatory nodules), and baseline patient reported

outcomes (VAS for pain, VAS for disease severity, and DLQI), will be collected. Baseline is defined as the visit 1, pre-injection assessment.

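### The HS-therapy and new-opioid exclusions stop at screening, leaving up to 21 days before the visit 1 baseline uncovered, most clearly for oral antibiotics and opioids

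*Combined protocol and SAP*

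**What the plan says.** Section 4.2 has four treatment-history exclusions that count back from screening, and the synopsis repeats those anchors:

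- Oral antibiotics: "Receipt of oral antibiotic treatment for HS within 28 days prior to screening".
- Topical therapy: "Receipt of prescription topical therapies for the treatment of HS within 14 days prior to screening, and systemic therapies for HS". The systemic part of the same criterion ends "hormonal therapies) within 28 days prior to screening".
- Opioids: "New intake of opioid analgesics starting within 14 days prior to screening".

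Major surgery, in the same list, is tied to dosing instead: "within 28 days prior to visit 1, Day 0 of start of study drug".

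Section 5.1 starts screening at the signing of consent and sets the limit "Visit 1 (day 0, must occur within 21 days of signing informed consent". Section 8.1 fixes the reference value: "Baseline is defined as the visit 1, pre-injection assessment". The secondary efficacy endpoints in sections 3.1 and 8.2 are all measured from that visit to visit 13.

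Section 2.8 governs other therapy on study. It bars anti-IL-1 and anti-TNF biologics, live virus vaccines and other investigational agents throughout. It allows one use, for acute exacerbation, of systemic HS therapies, intralesional or topical steroids, or laser or light. It names neither oral antibiotics nor opioids. Concomitant medications are recorded at screening and at visit 1 (sections 5.1 and 5.2).

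**The concern.** An exclusion of recent treatment helps the baseline only if it covers the time just before the baseline is taken. Here it can end up to three weeks earlier. HS runs in flares and remissions (section 1.2), so some patients could plausibly be treated between consent and visit 1.

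The study is open label and has no control group, so each patient's visit 1 value is the only comparator. A drug started in screening can distort the comparison in two ways. If it has already worked by visit 1, it lowers the baseline and makes later improvement harder to show. If it is still taking effect after visit 1, its benefit is counted as response to bermekimab. Section 1.2 presents the study as groundwork for later randomized studies, so the descriptive efficacy estimates will be used.

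**Working it through.** The plan states no figure to reproduce: section 10.2 gives a convenience sample with no calculation. The check is date arithmetic, a reading of whether another section closes the gap, and the weight of one patient.

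**1. Days not covered before baseline.** Inputs: look-backs of 28 and 14 days ending at screening (section 4.2); consent to visit 1 of at most 21 days (section 5.1). Days just before baseline outside the window = visit 1 date − consent date = 0 to 21, the same for all four exclusions.

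**2. Does anything else cover those days?**

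| Therapy | Section 4.2 after consent | Section 2.8 |
|---|---|---|
| Oral antibiotics for HS | no limit | not named |
| New opioids | no limit | not named |
| Systemic HS therapy | no limit | one use for acute exacerbation; unclear whether screening counts |
| Intralesional/topical steroids, laser/light | topicals: no limit; others not listed | as above |
| Anti-TNF and anti-IL-1 biologics | not part of this point | prohibited for the whole trial |

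No re-check of these exclusions at visit 1 is described, and no analysis rule uses a start during screening. HiSCR with its lesion counts, PGA, modified Sartorius and VAS are first scheduled at visit 1, so no scheduled earlier value would show a shift.

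**3. Effect within one patient (all counts and scores assumed).** The AN part of HiSCR needs a visit 13 count ≤ 0.5 × the baseline count.

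- Baseline already lowered: usual AN 6, reduced to 3 by visit 1. The threshold moves from 0.5 × 6 = 3 to 0.5 × 3 = 1.5, that is ≤ 1. A visit 13 count of 3 changes from meeting the AN part to missing it.
- Drug still taking effect: AN is 6 at visit 1 and the screening drug alone brings it to 3 by visit 13. Since 3 ≤ 0.5 × 6, the AN part is met with no contribution from bermekimab.
- Pain: a new opioid lowers pain VAS from 5 to 2 by visit 1. The patient drops out of the section 10.5.3 pain-reduction analysis, which requires a baseline of at least 3.

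**4. Effect on the group rate.** One patient is 1/10 = 10 percentage points in a group and 1/20 = 5 points pooled. Exact 95% limits are the 0.025 quantile of Beta(x, n − x + 1) and the 0.975 quantile of Beta(x + 1, n − x). Starting from 60%, the bermekimab rate reported for the earlier randomized study in section 1.1:

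| Responders | Rate | Exact 95% CI |
|---|---|---|
| 6/10 | 60% | 26% to 88% |
| 7/10 | 70% | 35% to 93% |
| 12/20 | 60% | 36% to 81% |
| 13/20 | 65% | 41% to 85% |

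**5. Two ways to close the gap.** Moving the anchor to visit 1 without other change would leave, after a full 21-day screening, only 28 − 21 = 7 days required before consent for the 28-day windows and none for the 14-day windows. Keeping the look-back and extending it through visit 1 gives up to 28 + 21 = 49 or 14 + 21 = 35 days.

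**The case against.** The strongest reply is that section 2.8 already handles part of this. The synopsis counts the three-week screening period within participation, so the single allowed use of steroids, retinoids, hormonal therapy or laser can be read to include screening. A course in screening would then use up that allowance, and a second rescue makes the patient a non-responder. The list is also open-ended, so leaving out antibiotics is not conclusive. This stands as a limit on scope: those therapies are restricted though not barred, and the gap is clearest for oral antibiotics and new opioids.

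A reader might also infer more than the documents support:

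- *That the plan delivers 0 drug-free days against an intended 14 or 28.* Zero is the worst case. The documents state no intended interval before baseline, and a patient who starts nothing in screening has at least the stated 14 or 28 days.
- *That HiSCR, AN change and pain VAS therefore do not measure the drug.* Only affected patients are concerned, and their number is unknown.
- *That the surgery criterion contradicts the others.* Different anchors for different purposes are not a contradiction. The surgery wording shows only that a visit 1 anchor is already in use.

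Two further points stand in part. If the entry criterion of at least 3 lesions is applied at visit 1, a patient lowered below 3 would not qualify; but section 4.1 does not say when it applies, and a patient lowered from 6 to 3 still would. And antibiotics and opioids are equally unnamed in section 2.8 after visit 1, so protecting the baseline does not by itself secure attribution up to visit 13.

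**Conclusion.** The point holds with limited scope. A site following the plan exactly can enroll a patient who began an oral antibiotic for HS or a new opioid up to 21 days before the only baseline. For systemic therapy, intralesional or topical steroids and laser or light, the position depends on whether section 2.8 reaches into screening, which is not stated.

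In affected patients, baseline AN, HiSCR or pain VAS may be confounded, in either direction. One misclassified patient changes HiSCR by up to 10 percentage points in a group of 10, or 5 points in the pooled 20. That is well inside the exact confidence intervals, but those intervals describe sampling error only and do not allow for a shifted baseline.

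This assumes that such starts occur, which the documents do not quantify, and that the drug changes lesion counts or pain. The endpoints are secondary and descriptive and the primary endpoint is safety. The change should be made, but the gap does not undermine the trial's main purpose.

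**What to change.** Keep the stated look-backs and extend each of the four exclusions through baseline, in both section 4.2 and the synopsis. For example: *within 28 days (14 days for prescription topicals and new opioids) prior to screening, or at any time between screening and visit 1 (Day 0)*. Simply re-anchoring to visit 1 is less good, because it would shorten the washout required before consent.

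Confirm the extended criteria against the concomitant-medication record already taken at visit 1. Reconcile section 2.8 with section 4.2 by stating whether the single allowed use covers the screening period.

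The cost is a wording amendment with no new procedure. Because visit 1 must fall within 21 days of consent, a 28-day interval after a start in screening cannot fit. A few patients treated in screening will therefore screen-fail, or need to re-consent and be screened again.
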